6.2.5. Patient Reported Outcomes Assessments

All patients are to complete the FCS Symptoms Two Week Recall at Screening and the FCS Symptoms and diet questionnaire on a daily basis for FCS symptoms/diet (minimum of 4 daily assessments per week) and every 4 weeks for FCS Impacts, and complete the PROMIS Adult Short Form v1.1 (Pain Interference 8a) every 4 weeks, for the duration of the study as outlined in Appendix A. Health-related quality of life (as measured by the PROMIS 29+2 Profile vs. 2.1) and an optional PROMIS[®] Short Form v2.0 – Cognitive Function 4a will be assessed at Baseline, 3 months, 6 months and end of study. Patient-reported global impression of severity (PGIS) will be administered at Baseline and every 4 weeks; the patient-reported global impression of change (PGIC) at 6 months and end of study. Patient-reported global impression of severity and PGIC are administered for purposes of PRO validation and estimation of minimal important difference (MID).

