FCS Impacts; Pain Interference Short Form 8a	х	Х	Х	Х	х	Х	х	Х	Х	х	Х	Х	Х	Х	Х	Х	Х	Х	Х	Х	Х	Х
Patient Global Impression of Severity (PGIS)			Х	Х	х	Х	х	Х	Х	Х	Х	Х	Х	Х	Х	Х	Х	Х	Х			
Patient Global Impression of Change (PGIC)									Х	х	Х							Х	Х			
Health-related Quality of Life (PROMIS 29+2 Profile v2.1). PROMIS Cognitive Function 4a (optional)			Х			Х			х	х	х							X	х			
Assessment of ER Visits, Hospitalization and Inpatient Days	Х	Х	Х	Х	х	Х	х	Х	Х	х	Х	Х	Х	Х	Х	Х	Х	Х	Х	Х	Х	Х
Adverse Events	Х	Х	Х	Х	Х	Х	Х	Х	Х	Х	Х	Х	Х	Х	Х	Х	Х	Х	Х	Х	Х	Х
Concomitant Medication	Х	Х	Х	Х	Х	Х	Х	Х	Х	Х	Х	Х	Х	Х	Х	Х	Х	Х	Х	Х	Х	Х
Diet/Alcohol Counseling ^M	Х		Х	Х		Х		Х		Х		Х		Х		Х			Х		Х	
Study Drug: SC Injection ^N			Х	Х	Х	Х	Х	Х		Х		Х	Х	Х	Х	Х	Х					

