- The Month 6 (primary analysis time point) score will be calculated from the non-missing scores from Weeks 23, 25 and 27 and the Month 12 score will be calculated from the non-missing scores from Weeks 49, 51 and 53. If all weekly scores during the period are missing, the missing Month 6 score will be imputed using the data from the week that is the closest to Day 169 and within $a \pm 30$ days window, the missing Month 12 data will be imputed using the data from the week that is the closest to the Day 351 and within $a \pm 30$ days window. If 2 or more visits with equal distance, then the average will be used.

ISIS 678354-CS3

Statistical Analysis Plan

The tables below list the summaries and analyses to be performed for the FCS impact score

Observed data			
Endpoint	Baseline	Post-baseline	Analysis
FCS Impacts – item score and composite score	Baseline is defined as the last non-missing assessment on or prior to the Day 1	If data is not available in a visit, the score will be considered as missing	Descriptive statistics of score, change and percent change over time in the FAS
		Month 6 (Primary analysis time point) - average of Weeks 23, 25, 27	1. Descriptive statistics of the impacts composite score, change and percent change at Month 6 and Month 12 in the FAS
		Month 12 -average of Weeks 49, 51 and 53	2. ANCOVA model of change from baseline in the impact composite score with the two stratification factors and treatment group as factors and the baseline score as a covariate in the FAS

Imputed data			
Endpoint	Baseline	Post baseline	Analysis
	Baseline is defined as the last non-missing assessment on or prior to the Day 1. If all pre-dose composite scores are missing, the baseline composite score will be considered as missing. Missing baseline will be imputed using the average of non-missing data from	Month 6 (Primary analysis time point) – average of Weeks 23, 25, 27 Month 12 -average of Weeks 49, 51 and 53 If all composite scores during the period are missing, the missing Month 6 score will be imputed using the data from the visit that is the	 Analysis Descriptive statistics of the impacts composite score, change and percent change at Month 6 and Month 12 in the FAS ANCOVA model of change from baseline in the impact composite score with the two stratification factors and treatment group as factors and the baseline score as a covariate in the FAS

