- The Month 6 (primary analysis time point) score will be calculated from the non-missing scores from Weeks 23, 25 and 27, the Month 12 pain interference score will be calculated from the non-missing scores from Weeks 49, 51 and 53, and the Month 12 PROPr domain and total scores and cognitive function score will be calculated from the non-missing scores from Weeks 51 and 53. If all scores during the period are missing, the missing Month 6 score will be imputed using the data from the week that is the closest to Day 169 and within a ± 30 days window, the missing Month 12 PROPr domain and total scores and cognitive function score will be imputed using the data from the week that is the closest to Day 169 and within a ± 30 days window, the missing Month 12 PROPr domain and total scores and cognitive function score will be imputed using the data from the week that is the closest to the Day 351 and within a ± 30 days window. If 2 or more visits with equal distance, then the average will be used.

The tables below list the summaries and analyses to be performed for the PROPr domain and
total scores, pain interference score, and cognitive function score

Observed data			
Endpoint	Baseline	Post-baseline	Analysis
PROMIS 29+2 domain and total scores, cognitive function scores	Baseline is defined as the last non-missing assessment on or prior to Day 1	If data is not available in a visit, the score will be considered as missing	Descriptive statistics of domain and total scores, change and percent change over time in the FAS
		Month 6 (Primary analysis time point) - average of Weeks 23, 25, 27	1. Descriptive statistics of the domain and total scores, change and percent change at Month 6 and Month 12 in the FAS
		Month 12 -average of Weeks 51 and 53	2. ANCOVA model of change from baseline in the domain and total scores with the two stratification factors and treatment group as factors and the corresponding baseline score as a covariate in the FAS

ISIS 678354-CS3

Observed data			
Endpoint	Baseline	Post-baseline	Analysis
Pain interference	Baseline is defined as the last non-missing assessment on or prior to Day 1	If data is not available in a visit, the score will be considered as missing	Descriptive statistics of score, change and percent change over time in the FAS

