		Month 6 (Primary analysis time point) - average of Weeks 23, 25, 27 Month 12 -average of Weeks 49, 51 and 53	 Descriptive statistics of the scores, change and percent change at Month 6 and Month 12 in the FAS ANCOVA model of change from baseline with the two stratification factors and treatment group as factors and the corresponding baseline score as a covariate in the FAS

Imputed data			
Endpoint	Baseline	Post-baseline	Analysis
PROMIS 29+2 domain and total scores, cognitive function scores	Baseline is defined as the last non-missing assessment on or prior to Day 1. If all pre-dose scores are missing, the baseline score will be considered as missing. Missing baseline will be imputed using the average of non-missing data from other patients in the same stratification category	Month 6 (Primary analysis time point) - average of Weeks 23, 25, 27 Month 12 -average of Weeks 51 and 53 If all scores during the period are missing, the missing Month 6 score will be imputed using the data from the visit that is the closest to Day 169 and within $a \pm 30$ days window, the missing Month 12 data will be imputed using the data from the week that is the closest to the Day 358 and within $a \pm 30$ days window. If 2 or more visit with equal distance, then the average will be used.	 Descriptive statistics of the domain and total scores, change and percent change at Month 6 and Month 12 in the FAS ANCOVA model of change from baseline in the domain and total scores with the two stratification factors and treatment group as factors and the corresponding baseline score as a covariate in the FAS

ISIS 678354-CS3

Statistical Analysis Plan

Imputed data			
Endpoint	Baseline	Post-baseline	Analysis

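### For PROMIS 29+2 and cognition (Months 6 and 12) and for FCS Impacts and pain interference (Month 12), the ±30-day nearest-score rule has no other scheduled visit to borrow from, so the imputed analysis nearly repeats the observed-case one

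*Combined protocol and SAP*

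**What the plan says.** SAP 4.11.3.4 (FCS Impacts) and 4.11.3.5 (PROMIS instruments) each describe an ANCOVA on observed data and then, in addition, the same ANCOVA in the FAS after imputation. Missing baselines are filled with the mean of other patients in the same stratification category. A post-baseline value is filled only when every visit that makes up the time point is missing.

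- **Month 6** (average of Weeks 23, 25 and 27), all instruments: "the missing Month 6 score will be imputed using the data from the week that is the closest to Day 169 and within a" ±30-day window.
- **Month 12, FCS Impacts** (Weeks 49, 51 and 53): "the missing Month 12 data will be imputed using the data from the week that is the closest to the Day 351", again within ±30 days. The pain interference table gives the same visits and the same anchor.
- **Month 12, PROMIS 29+2 and cognition** (Weeks 51 and 53): the text of 4.11.3.5 has "closest to the Day 351 and within a ± 30 days window", while the imputed-data table has "closest to the Day 358 and within" ±30 days.

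On the schedule, protocol 6.2.5 says that PROMIS 29+2 and the optional cognition form "will be assessed at Baseline, 3 months, 6 months and end of study". The Appendix A row "Health-related Quality of Life (PROMIS 29+2 Profile v2.1). PROMIS Cognitive Function 4a (optional") is marked at Weeks 1, 13, 23, 25, 27, 51 and 53 and nowhere in follow-up. FCS Impacts and pain interference are marked at every visit, including follow-up Weeks 4, 8 and 13.

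**The concern.** A nearest-score rule needs a neighbouring score. For the daily diary (SAP 4.11.3.3) the same rule is sensible, because there is a score every week. PROMIS 29+2 is sparse: its Month 6 and Month 12 visits are clusters with long gaps on either side. The rule starts only when the whole cluster is missing, so what matters is whether any visit outside the cluster lies within 30 days of the anchor. If none does, patients with no score at the time point are left out of both analyses. Close agreement between the two would then follow almost automatically, and could be read as reassurance that dropout did not drive the quality-of-life, impact or pain-interference results.

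**Working it through.** **Inputs.** Anchors, ±30 days and averaged visits: SAP 4.11.3.4 and 4.11.3.5, text and tables. Visit days and tolerances: protocol Appendix A. Analysis windows: SAP 4.2.4. Follow-up is counted from one dosing interval after the last dose (Appendix A footnote P).

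**1. The calendar reproduces the SAP's own figure.** The last dose is at Week 49, Day 337. End of treatment is 337 + 28 = Day 365, and follow-up Week 4 is 365 + 28 = Day 393. The midpoint (365 + 393)/2 = 379 matches the footnote to the SAP 4.2.4 window table.

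**2. Search windows.** 169 ± 30 = Days 139–199; 351 ± 30 = Days 321–381; 358 ± 30 = Days 328–388.

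**3. Scheduled visits left after removing the averaged ones.**

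| Score and time point | Window (days) | Scheduled donors | Nearest other scheduled visit |
|---|---|---|---|
| PROMIS 29+2, cognition, Month 6 | 139–199 | 0 | Week 13, Day 85: 169 − 85 = 84 days away |
| PROMIS 29+2, cognition, Month 12 (anchor 351) | 321–381 | 0 | Week 27, Day 183: 351 − 183 = 168 days away |
| PROMIS 29+2, cognition, Month 12 (anchor 358) | 328–388 | 0 | Week 27: 358 − 183 = 175 days away |
| FCS Impacts, pain interference, Month 12 | 321–381 | 0 | Week 45, Day 309, and follow-up Week 4, Day 393: 42 days away each |
| FCS Impacts, pain interference, Month 6 | 139–199 | 2 | Week 21, Day 141, and Week 29, Day 197: 28 days away each |

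**4. Visit tolerance.** With ±3 days, Week 45 is at latest Day 312 (below 321) and follow-up Week 4 at earliest Day 390 (above 381). The PROMIS gaps are far larger. The zeros stand.

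**5. Days left for unscheduled forms.** Subtract the SAP 4.2.4 analysis windows of the averaged visits, because a form on those days already counts as observed.

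- PROMIS Month 6 (Days 149–190 taken): Days 139–148 and 191–199 remain.
- PROMIS Month 12 (Days 331–379 taken): Days 321–330 and 380–381 remain, or Days 328–330 and 380–388 with anchor 358.
- Impacts and pain interference, Month 12 (Days 324–379 taken): Days 321–323 and 380–381 remain.

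SAP 4.2.4 assigns the leftover PROMIS days to no analysis visit, so it is unclear which week would be borrowed. For Impacts and pain interference, Days 321–323 map to Week 45. The SAP does not say whether distance runs from the actual or the target day; measured from Week 45's target day (309) they would not qualify.

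**6. Early-termination visits.** Protocol 8.8.1 asks patients who stop treatment early and do not attend the landmark visits to complete the Week 53 assessments, which include PROMIS 29+2, ideally within 2 weeks of the last dose. After a Week 21 dose (Day 141) that is Days 141–155: Days 141–148 could serve the rule, and Days 149–155 already map to Week 23. After a Week 29 dose (Day 197), only Days 197–199 could serve. For Month 12, after a Week 45 dose (Day 309), the range is Days 309–323, of which Days 321–323 qualify with anchor 351 and none with anchor 358.

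**The case against.** The strongest reply is that the table in step 3 uses the calendar of patients who complete treatment, whereas the rule exists for those who do not.

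Follow-up visits move earlier when dosing stops early. With a last dose at Week 45 (Day 309), follow-up Week 4 falls on 309 + 28 + 28 = Day 365. With a last dose at Week 41 (Day 281), follow-up Weeks 4 and 8 fall on Days 337 and 365. Impacts and pain interference are collected at those visits, and by day the scores map to Week 49 or Week 53. This stands, so it would be wrong to infer that everyone who stops early is missing from both analyses. But such scores enter through the visit windows as observed data, not through the ±30-day rule, and PROMIS 29+2 has no follow-up assessments at all.

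Appendix A also labels its last treatment column as the treatment early-termination visit, so a PROMIS form at withdrawal is planned, and visits can be displaced under the public-health allowances in protocol 3.7. This stands too. A reader might infer that the search windows contain no scheduled visit, or that the rule can never fill a value. The documents support neither: the windows contain the averaged visits themselves, and a form can land in the strips in step 5.

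Finally, the endpoints are exploratory (protocol 1.2.3, SAP 3.2.3), cognition is optional, and the SAP does not call the imputed analysis a sensitivity analysis. A reader might infer that the SAP claims robustness to dropout; it does not. The risk lies in how agreement between the two analyses would be read.

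**Conclusion.** The point holds for PROMIS 29+2 and cognition at both time points, and for FCS Impacts and pain interference at Month 12: no scheduled donor in any of these cases, whichever PROMIS anchor is used. Out of 61 days searched (2 × 30 + 1), unscheduled forms could be borrowed on at most 19 days (PROMIS Month 6: 10 + 9), 12 days (PROMIS Month 12: 10 + 2, or 3 + 9 with anchor 358) or 5 days (Impacts and pain interference Month 12: 3 + 2). Apart from imputed baselines, the second ANCOVA is nearly the observed-case one.

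Impacts and pain interference at Month 6 are not affected. None of these endpoints is in the testing sequence of SAP 4.9.1.3, so the primary and ranked secondary results are untouched. The documents give no expected missing rate for these scores, so the number of patients concerned is unknown. The conclusion assumes nominal visit days with the stated tolerance, and mapping by day as in SAP 4.2.4. The sentence on this rule in 4.11.3.5 repeats a clause, possibly from PDF reading; nothing here depends on that.

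**What to change.** For these scores, replace the ±30-day substitution with multiple imputation by treatment group, using all scheduled scores of the same instrument and the two stratification factors, as in step 1 of SAP 4.9.1.2. Two adaptations are needed:

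- **Scale.** Impute on the original scale. Section 4.9.1.2 log-transforms lipids, but the Impacts composite and PROPr can both equal 0.
- **Reference-based step.** State whether the jump-to-reference replacement in steps 2 and 3 applies to these scores.

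If a nearest-visit rule is kept for Impacts and pain interference at Month 12, widen it to ±45 days (Days 306–396) and restrict donors to treatment-period visits. Without that restriction, Week 45 and follow-up Week 4 tie at 42 days and the SAP's tie rule would average an on-treatment with a post-treatment score.

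Use one Month 12 anchor for PROMIS in text and table. The cost is SAP wording, some programming and slightly wider intervals where values are truly imputed; no new data are needed.

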4.2.2. Baseline Consideration

Baseline for lipid measurements is defined as the average of the pre-dose measurement on Day 1 and the last measurement closest to Day 1 (last measurements from Qualification period and Screening period), prior to administration of the first dose of Study Drug. If 1 of the 2 measurements is missing, then the other measurement will be assigned as the baseline value. If all pre-dose measurements are missing, then the baseline will be set as missing. Missing baseline values will be imputed using the multiple imputation method described in Section 4.9.1.2 in the SAP. Note that if on Day 1, there are multiple pre-dose assessments, then the last assessment with non-missing value will be used as the Day 1 pre-dose assessment.

Baseline consideration for exploratory endpoints:

- 1. Average worst FCS Symptoms (abdominal pain, physical fatigue, difficulty thinking, diarrhea, and composite symptom score): baseline is defined as the average during the screening period and up to Day 1; an alternative baseline is defined as single observation collected at the first day of screening with a two-week recall.
- 2. Highest worst FCS Symptoms: baseline is defined as the highest (worst) score during the screening period and up to Day 1.
- 3. FCS Impacts, PROMIS pain interference, HR-QoL (PROMIS 29+2 Profile v2.1), PROMIS cognitive function, and Patient Global Impression of Severity (PGIS): baseline is defined as the last non-missing assessment on or prior to Day 1

ISIS 678354-CS3

The ECG measurements will be performed in triplicate at each visit. Baseline for continues variables is defined as the average of the last non-missing triplicate prior to the first dose of Study Drug.; Baseline for categorical variable is defined as the worst of the last non-missing triplicate prior to the first dose of Study Drug. If only one or two measurements are available, the baseline will be determined from the available measurements.

The baseline for platelet is defined as the average of all assessments prior to the first dose of Study Drug.

The baseline for other measurements is defined as the last non-missing assessment prior to the first dose of Study Drug.

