4.11.3. Additional/Exploratory Analysis

4.11.3.1. Percent Change in Fasting TG, apoC-III, apoB-48, and non-HDL-C at Month 3

The following tertiary/exploratory endpoints will be compared between ISIS 678354 treatment group (ISIS 678354 80 mg, ISIS 678354 50 mg) and placebo using an ANCOVA model with the percent change in original scale as the dependent variable, two stratification factors and treatment group as factors, the corresponding log-transformed baseline fasting results as covariates in the FAS. The same multiple imputation method as the primary analysis of the primary endpoint will be used for imputing missing data.

- Percent change in fasting TG from Baseline at Month 3
- Percent change in fasting apoC-III from Baseline at Month 3
- Percent change in fasting apoB-48 from Baseline at Month 3
- Percent change in fasting non-HDL-C from Baseline at Month 3

The change and percent change from Baseline in fasting TG, apoC-III, apoB-48, and non-HDL-C will be summarized by treatment group over time.

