Pain interference	Baseline is defined as the last non-missing assessment on or prior to Day 1. If all pre-dose composite scores are missing, the baseline composite score will be considered as missing. Missing baseline will be imputed using the average of non-missing data from other patients in the same stratification category	Month 6 (Primary analysis time point) - average of Weeks 23, 25, 27 Month 12 -average of Weeks 49, 51 and 53 If all composite scores during the period are missing, the missing Month 6 score will be imputed using the data from the visit that is the closest to Day 169 and within $a \pm 30$ days window, the missing Month 12 data will be imputed using the data from the week that is the closest to the Day 351 and within $a \pm 30$ days window. If 2 or more visits with equal distance, then the average will be used.	 Descriptive statistics of the score, change and percent change at Month 6 and Month 12 in the FAS ANCOVA model of change from baseline with the two stratification factors and treatment group as factors and the corresponding baseline score as a covariate in the FAS

4.11.3.6. The Patient Global Impression of Severity Scale (PGIS) score and Patient Global Impression of Change (PGIC) Score

The PGIS score (scaled None = 0, Mild = 1, Moderate = 2, Severe = 3, and Very severe=4), change from baseline in PGIS, and PGIC score (scaled Much better = 1, A little better= 2, No change = 3, A little worse = 4, and Much worse =5) will be tabulated by severity or change category and by treatment group over time.

Change from baseline in PGIS at the primary time point (average at Weeks 23, 25, 27) and at Month 12 (average of Weeks 51 and 53) will be classified to 2 categories: improved (defined as change from baseline ≤ 0) and not improved (defined as change from baseline ≥ 0). The data will be analyzed using a logistic regression model with the two randomization stratification factors and treatment group as factors and baseline PGIS score as a covariate, and will be conducted in the FAS.

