PGIC score at the primary time point (average at Weeks 23, 25, 27) and at Month 12 (average of Weeks 51 and 53) will be classified to 2 categories: improved (defined as PGIC score = Much better [< 1.5] or A little better [1.5 to < 2.5]) and not improved (PGIC score = No change [2.5 to < 3.5], A little worse [3.5 to < 4.5], Much worse [\geq 4.5]) and analyzed using a logistic regression model with the two randomization stratification factors and treatment group as factors and baseline PGIS score as a covariate, and will be conducted in the FAS.

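### The PGIS responder rule counts an average change of exactly 0 as both improved and not improved

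*Combined protocol and SAP*

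**What the plan says.** SAP 4.11.3.6 turns the PGIS change into a binary outcome at two time points. Month 6 uses the Week 23, 25 and 27 assessments ("Change from baseline in PGIS at the primary time point (average at Weeks 23, 25, 27") and Month 12 uses Weeks 51 and 53. The rule is "improved (defined as change from baseline ≤ 0) and not improved (defined as change from baseline ≥ 0". The result goes into a logistic regression in the FAS, with treatment group and the two stratification factors as factors and baseline PGIS as covariate.

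Three other statements bear on the rule:

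- The scale is an integer scale on which higher is worse: "The PGIS score (scaled None = 0, Mild = 1, Moderate = 2, Severe = 3, and Very severe=4". Improvement is therefore a negative change.
- Baseline is one assessment, not an average (SAP 4.2.2): "Patient Global Impression of Severity (PGIS): baseline is defined as the last non-missing assessment on or prior to Day 1".
- The companion rule for the Patient Global Impression of Change (PGIC), also in SAP 4.11.3.6, uses bins that do not overlap and puts unchanged patients on one side only: "not improved (PGIC score = No change [2.5 to < 3.5".

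**The concern.** A logistic regression needs one value, 0 or 1, for each patient. The printed rule gives a unique value to every patient whose average change is below or above 0. A patient at exactly 0 gets two. Neither a tie rule nor sample code for this analysis settles the matter, so whoever writes the program has to decide. Unchanged patients may then be coded by accident of programming order, or the coding may be settled after treatment codes are known. A reader with only the SAP could not reproduce the result.

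The stakes are limited to this analysis. It sits under "4.11.3. Additional/Exploratory Analysis", outside the 28 ranked secondary comparisons in SAP 4.9.1.3. Protocol 6.2.5 gives a supporting purpose for the two global scales: "PGIC are administered for purposes of PRO validation and estimation of minimal important difference (MID".

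**Working it through.** **1. The two sets.** Let d be the average of the post-baseline scores minus the baseline score.

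- Improved: d ≤ 0.
- Not improved: d ≥ 0.
- Overlap: d = 0 and nothing else. Every other value falls in exactly one category.

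The same text gives two different programs. If the first condition is tested first, every patient with d = 0 is improved. If the second is tested first, every such patient is not improved.

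**2. Is d = 0 attainable?** Inputs are the 0 to 4 integer scale (SAP 4.11.3.6), the single-assessment baseline b (SAP 4.2.2), three visits at Month 6 and two at Month 12. With complete visits and integer scores, d = 0 when the visit scores sum to 3b at Month 6 or to 2b at Month 12. Enumerating all patterns gives:

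| Baseline b | Month 6: d < 0 | Month 6: d = 0 | Month 6: d > 0 | Month 12: d < 0 | Month 12: d = 0 | Month 12: d > 0 |
|---|---|---|---|---|---|---|
| 0 | 0 | 1 | 124 | 0 | 1 | 24 |
| 1 | 10 | 10 | 105 | 3 | 3 | 19 |
| 2 | 53 | 19 | 53 | 10 | 5 | 10 |
| 3 | 105 | 10 | 10 | 19 | 3 | 3 |
| 4 | 124 | 1 | 0 | 24 | 1 | 0 |
| Total | 292 | 41 | 292 | 56 | 13 | 56 |

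Checks: 292 + 41 + 292 = 625 = 5 × 125, and 56 + 13 + 56 = 125 = 5 × 25.

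A tie is possible from every baseline level, and it always includes the patient who gives the baseline rating again at each visit. At baseline 0 (no symptoms) a negative change is impossible, so the tie is the only way to meet the improved definition at all.

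The counts give every pattern equal weight. They show that ties are attainable; they do not estimate how many patients will tie.

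**3. What one tied patient is worth.** The lay summary at the front of the document gives 22 patients on 80 mg, 21 on 50 mg and 23 on placebo. Assuming all have evaluable PGIS data, recoding one unchanged patient moves the arm's improved proportion by 1/22 = 4.5, 1/21 = 4.8 or 1/23 = 4.3 percentage points. The documents do not say how many patients were unchanged in each arm, so neither the size nor the direction of the effect on the odds ratio can be given.

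**4. Is the tie resolved elsewhere?** Protocol 6.2.5 covers purpose and timing, Protocol Appendix A the visits, SAP 4.2.2 the baseline, SAP 4.2.3 the averaging of non-missing assessments and SAP 4.2.4 the visit windows. None assigns a change of 0 to a category.

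**The case against.** Four points can be made for the plan as it stands.

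- **The symbol may be a conversion error.** The text was read from PDF and contains other single-character errors. If the original page shows a strict sign in the first inequality, the point disappears. Against that, strict signs come through correctly in the PGIC rule that follows, which makes a misreading less likely without ruling it out. This doubt stands.
- **The PGIC rule does not dictate the repair.** PGIC places the whole band from 2.5 to below 3.5 under not improved. Ratings of 3, 3 and 2 average 2.67 and count as not improved, whereas a PGIS patient with baseline 2 and visits 2, 2 and 1 has d = −0.33 and would count as improved under a strict rule. In the same enumeration, d = −0.33 covers 0 + 6 + 18 + 15 + 3 = 42 Month 6 patterns, and d = −0.5 covers 0 + 2 + 4 + 4 + 2 = 12 Month 12 patterns. This is correct: the two scales would agree on exact no-change, not across the band. It does not make a strict rule unsound, since the ordinary meaning of improved also excludes no change.
- **The pattern counts assume complete integer scores.** Missing visits, or two equally near assessments averaged within a window, alter them. That is true, but ties remain attainable.
- **Other output shows the unchanged patients.** SAP 4.11.3.6 also tabulates PGIS change by category over time. This helps a reader of the report but does not tell the regression how to code a tie.

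**Conclusion.** The rule contradicts itself at one value, and that value is an ordinary one on this scale. Patients with an average PGIS change of exactly 0 have no unique outcome in the Month 6 and Month 12 regressions.

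The severity is minor. Type I error control and the primary, secondary and safety conclusions are unaffected. The effect on the PGIS odds ratio is not estimable from the documents. Confidence is medium, because the conclusion assumes that the inequality signs in the extracted text match the original page.

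**What to change.** Check the original page first. If it reads as extracted, define improved as change from baseline < 0 and leave not improved as change from baseline ≥ 0. This gives every value one category and treats exact no-change as the PGIC rule does. Then confirm that the program codes it that way at both time points.

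If the SAP is no longer to be revised, one sentence in the clinical study report stating which rule was used is enough. SAP Section 1 already requires deviations to be documented there. The cost is one inequality sign and a program check, or that one sentence.
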